Limitations of DRA. Although highly effective, DRA has a number of limitations¹⁷⁻²¹ that compromise its effectiveness when implemented by caregivers in the natural environment. In the latter stages of DRA, caregivers are trained to implement treatment, and it is critical that they do so with high procedural integrity (e.g., 90% accuracy), which is more likely if the intervention is practical and compatible with their daily routine. Researchers have identified two important practical limitations of DRA that can interfere with accurate caregiver implementation, namely that treated individuals request reinforcement via the FCR (a) at exceedingly high rates (e.g., request to escape every adult directive) or (b) when it is difficult for the caregiver to deliver reinforcement (e.g., requesting attention when a parent is changing an infant sibling). Our research team and others have used reinforcer-schedule thinning procedures to address these limitations and improve the practicality of DRA.^{21,23} Reinforcer schedule thinning involves progressively and systematically reducing the amount of reinforcers available during treatment sessions. This process is conducted in order to prepare the treatment to be practically used when reinforcers cannot always be feasibly delivered. Unfortunately, in the first large study on reinforcer-schedule thinning, we found that DRA was ineffective in 14 of 25 applications when schedule thinning reached a practical endpoint.²¹ In most cases, it was necessary to add a more restrictive and intrusive punishment component to DRA in order to thin the schedule and also maintain low rates of destructive behavior. A recent replication of this large study reported somewhat more favorable outcomes, but DRA plus schedule thinning still only maintained a 90% reduction from baseline in 11 of 23 applications (48%).²³ In addition, other recent studies have found that when participants treated with DRA were subsequently exposed to extinction of the FCR (or thin reinforcement schedules), treatment relapse often occurred in the form of resurgence of destructive behavior.²⁴⁻²⁶ Similarly, in the first large scale study examining the prevalence of resurgence during schedule thinning, we found that resurgence occurred in 19 out of 25 applications or 76%.²⁷ Collectively, the limitations stated above are evidence for continued refinement to DRA procedures to increase efficacy. In the same way, it is imperative that we develop more durable procedures that will reduce the likelihood of resurgence (i.e., relapse of destructive behavior). These limitations of DRA are actually predicted by a quantitative model derived from behavioral momentum theory. Behavioral momentum theory is a quantitative theory that predicts that DRA, as it is typically implemented, actually promotes resurgence and resistance to extinction for destructive behavior when the FCR is exposed to extinction or thin reinforcement schedules. More importantly, behavioral momentum theory provides clear quantitative guidance on how DRA procedures might be altered in order to mitigate or prevent treatment relapse.²⁸ Several lines of research have used behavioral momentum theory as a guide to develop more efficacious DRA procedures. Unfortunately, recent developments suggest that behavioral momentum theory may not

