We will develop and then assess an alternative schedule-thinning progression for use with children receiving DRA for destructive behavior that we predict to greatly reduce or prevent resurgence of destructive behavior during schedule thinning. One advantage of RaC over BMT is that with RaC we can update our prediction model dynamically after each session during schedule thinning. The prediction of RaC regarding how many reinforcers should be programmed for the next session would change as a result of this recent episode of responding (or lack thereof). We will use this feature of RaC to guide schedule thinning in our test group. The control group will be based on typical responding during reinforcer-schedule thinning observed in the published literature, much of which is based on research from our own clinic (see below). Thus, we do not intend to enroll participants prospectively into the control group. Baseline, DRA training, DRA, and stimulus context. Baseline, DRA training, and DRA procedures will be identical to those conducted in Experiment 1 except that destructive behavior and the alternative response (i.e., the FCR) will be reinforced on a continuous (or near-continuous) schedule in baseline and DRA sessions, respectively. DRA training will be conducted in a manner identical to the procedures used in Experiment 1. The baseline and DRA sessions will continue until the stability criteria specified for Experiment 1 are met. All sessions will be conducted within one stimulus context, as described above.

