DRA schedule thinning. Following an initial demonstration of the efficacy of DRA in which the participant is taught the FCR to access the reinforcer maintaining problem behavior, we will initiate DRA schedule thinning by introducing and then systematically lengthening periods of time in which that reinforcer is unavailable. Periods in which the reinforcer is available and unavailable will be signaled using strategies most relevant to the child's treatment and skill-level, such as different colored stimuli (e.g., green and red wristbands), the presentation and absence of work materials, or the presentation and absence of the communication materials. For schedule-thinning steps, we will use the quantitative models of RaC Theory and the results of a corresponding study with nonhuman animals to dynamically adjust each upcoming schedule-thinning step. We will use additional teaching procedures (e.g., prompting, blocking) as necessary to facilitate schedule thinning, as we would clinically. DRA schedule thinning will continue until the stability criteria specified for Experiment 1 are met under terminal schedules that are similar to those found within our control group. We will then compare these data to a control group consisting of the published data depicted in Briggs et al.²⁷ and reviewed by Saini et al.⁴² We will compare our results from the test group in the current study to the published data to determine whether RaC-informed schedule thinning substantially reduced resurgence compared to traditional schedule-thinning methods published in the literature.

B. Data Points

Dependent variables and measurement. The primary dependent measure will be the rate of destructive behavior (aggression, property destruction, self-injurious behavior) assessed via direct observation. Aggression will be defined as forceful pushing or striking others with body parts (e.g., pushing, hitting, kicking, head-butting), hitting others with objects or throwing objects at others, pinching, scratching, or biting. Property destruction will be defined as forceful banging, throwing, overturning, tearing or climbing on objects not made for that purpose. Self-Injurious Behavior will be defined as forceful striking, scratching, rubbing, poking or biting ones own body parts such that

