4.3 Number of Subjects

A. Total Number of Subjects

We conservatively estimate at least 60% of patients receiving clinical treatment in our program will meet the inclusion criteria. During the project, we will recruit 22 (12 for study 1 and 10 for Study 2) and retain 20 children with severe destructive behavior. We expect 10% attrition.

B. Total Number of Subjects If Multicenter Study

Not Applicable

C. Feasibility

We will recruit 22 and retain 20 children with severe destructive behavior from the Severe Behavior Program. We will recruit 12 and retain 11 children for Study 1, and we will recruit 10 and retain 9 children for Study 2. We conservatively estimate at least 60% of patients will meet the criteria (n = 45 per year available; eight per year needed, maximum). The research team will communicate the recruitment plan to all case managers in the Severe Behavior Program so that case managers can recommend relevant participants. The principal investigator and research staff will meet to discuss recruitment status and resolve any issues related to recruitment.

Additionally, the DDDC has 10 classes with a class size between 5 and 8 patients. Thus, the DDDC has between 50 and 80 patients at a given time. The majority of patients have a diagnosis of ASD, and a large minority of patients are reported to display destructive behavior. We expect that roughly 5-10 patients will be appropriate for the study, and recruitment is deemed feasible.

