## Statistical Plan

### Experiment 1

We will collect interobserver agreement on at least 33% of all sessions and ensure that the second data collector is blind to the study aims and hypotheses on one half of those observations. For Exp. 1, we will compare magnitudes of resurgence for the three treatment durations observed during the first five sessions of each resurgence test. We will report findings for each sex, in addition to reporting our aggregated data across sexes. We will apply a general linear model with two within-subject variables (individual session number and treatment duration) and one between-groups variable (treatment-duration sequence). We expect large differences between the extended-DRA condition and the short-DRA condition and a small-to-nonsignificant effect for the other paired comparisons (i.e., short vs. moderate and moderate vs. extended). Finally, model fits and comparisons for RaC and BMT will be conducted.

### Experiment 2

We will compare the prevalence and magnitude of resurgence during this RaC-informed schedule-thinning progression to that observed in the control group. We will calculate odds ratios for the likelihood of resurgence with and without RaC information on a per-case and on a per-schedule-step basis. We will apply Fisher's exact-probability statistic to test the significance of the odds ratios. With a minimum expected reduction in the per-case prevalence of 50% across 12 participants, we estimate a power of 0.89 with alpha=0.05. In addition, on a per schedule-step basis, the power increases to 0.98 with alpha=0.05. We will assess the adequacy of RaC and BMT in describing the data. Because BMT is not equipped to incorporate dynamic changes in DRA, we expect this model to poorly describe the data. RaC, however, easily incorporates such dynamic changes, and we expect the model to provide a good description of the data.

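### The stated per-case power of 0.89 for Experiment 2 does not follow from Fisher's exact test with the protocol's own control figures

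*SAP*

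**What the plan says.** The SAP (Statistical Plan, Experiment 2) says: "With a minimum expected reduction in the per-case prevalence of 50% across 12 participants, we estimate a power of 0.89 with alpha=0.05". Protocol section 1.5 gives the same sentence as its sample size justification. On the test, the SAP says: "We will apply Fisher's exact-probability statistic to test the significance of the odds ratios".

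The comparison group is historical. Protocol section 1.3 says that "we do not intend to enroll participants prospectively into the control group", and also "We will then compare these data to a control group consisting of the published data depicted in" one prevalence study, together with data reviewed in a second cited source. Section 1.1 reports the result of that prevalence study: "we found that resurgence occurred in 19 out of 25 applications or 76" per cent.

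On numbers, protocol section 4.3 says "we will recruit 10 and retain 9 children for Study 2"; the 12 in that section is the recruitment target for Study 1.

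The power sentence does not give the control prevalence, the number of controls, the sidedness of the test, or whether 50% is relative or in percentage points.

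**The concern.** A reader who takes the control prevalence from section 1.1, halves it and applies the named test with 12 cases gets a figure far below 0.89. Apart from a per-step power of 0.98, this sentence is the whole quantitative case for the size of Experiment 2. The 0.98 cannot be checked, because no step counts or per-step rates are given.

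A power of 0.89 implies that a true effect of the stated size would be missed about 11 times in 100. If power is 0.57, it would be missed about 43 times in 100. Readers who rely on the printed figure would give a non-significant per-case result more weight than it can bear.

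**Working it through.** **Inputs**
- Test cases: n₁ = 12 (power sentence); also 10 and 9 (protocol 4.3).
- Control prevalence: p₂ = 19/25 = 0.76 (protocol 1.1).
- Controls: n₂ = 25 is the only count printed. It was varied up to 1000 because a second source is named.
- Effect: relative reading p₁ = 0.76 × 0.5 = 0.38; percentage-point reading p₁ = 0.76 − 0.50 = 0.26.
- Alpha 0.05. Sidedness is not stated, so both were run.

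**Formula**

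Power = Σₐ Σ_b Bin(a; n₁, p₁) × Bin(b; n₂, p₂), summed over all tables with a/n₁ < b/n₂ and Fisher p ≤ 0.05.

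**Attempt to reproduce 0.89 with 12 cases and controls at 76%**

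| Controls | 38%, two-sided | 38%, one-sided | 26%, two-sided | 26%, one-sided |
|---|---|---|---|---|
| 25 | 0.569 | 0.616 | 0.818 | 0.849 |
| 40 | 0.643 | 0.680 | 0.883 | 0.895 |
| 50 | 0.657 | 0.697 | 0.890 | 0.908 |
| 100 | 0.729 | 0.755 | 0.929 | 0.941 |
| 200 | 0.762 | 0.789 | 0.947 | 0.956 |
| 1000 | 0.794 | 0.812 | 0.958 | 0.964 |

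Under relative halving no row comes near 0.89, because the 12 test cases are the limit. Under the 50-point reading 0.89 appears at about 40 to 50 controls, but not at 25.

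**Hand check.** Hold the controls at 19/25. Two-sided Fisher p is 0.027 for 4/12 and 0.067 for 5/12, so significance needs at most 4 resurgences in 12. P(X ≤ 4 | 12, 0.38) = 0.496 and P(X ≤ 4 | 12, 0.26) = 0.821, in line with the first row.

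**Effect that would give 0.89.** With 12 against 25 at 76%, two-sided power is 0.89 when p₁ is about 0.21, a relative reduction of (0.76 − 0.21)/0.76 = 72%.

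**Other routes to about 0.89**
- A one-sided, one-sample exact binomial test against a fixed 76% rejects at 6 or fewer of 12 (size 0.045). Its power at 38% is P(X ≤ 6 | 12, 0.38) = 0.875. This is not the SAP's test, and it ignores sampling error in the controls.
- A one-sided arcsine approximation with a 50-point drop, 12 against 25, gives 0.910. This is not Fisher's test either.
- With the controls held at 19/25, a one-sided Fisher test rejects at 5 or fewer of 12. A 50-point drop then gives 0.935, above 0.89; halving gives 0.717.
- Halving from a higher control prevalence, two-sided, 12 against 25, gives 0.64 from 80%, 0.81 from 90% and 0.90 from 95%.

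**At the Study 2 size in protocol 4.3 (two-sided)**

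| Cases | Controls | 76% to 38% | 76% to 26% |
|---|---|---|---|
| 10 | 25 | 0.465 | 0.711 |
| 9 | 25 | 0.474 | 0.716 |
| 10 | 50 | 0.566 | 0.817 |
| 9 | 50 | 0.533 | 0.781 |

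The slightly higher values for 9 than for 10 cases against 25 controls come from the discreteness of the exact test.

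**The case against.** The strongest reply is that the plan never limits the controls to 25 and never says that 50% is relative. Protocol section 1.3 names a second source, and section 1.6 says that the literature will be searched for suitable studies. The 76% comes from only one of these sources, so the pooled prevalence may differ. A prevalence is itself a percentage, so a 50-point drop is a possible reading, and with about 50 controls the named test then gives 0.890 two-sided.

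This stands, and it rules out a stronger claim that a reader might infer: that 0.89 is impossible under every reading, or that 0.57 is the true power. The documents do not fix enough inputs for either. The reply does not rescue the printed sentence, however. It needs a control number that appears nowhere in the plan, and it turns a minimum expected reduction of 50% into a relative reduction of about two thirds (0.50/0.76 = 66%).

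A reader might also infer that a non-significant Fisher result would stop the follow-on randomized trial. Protocol section 1.10 makes that trial depend on the new procedure being found more effective, but does not tie this to the per-case p-value. The SAP also plans comparisons of magnitude and per schedule step. How a non-significant per-case result would be read is not stated.

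**Conclusion.** The point holds in this form: the per-case power of 0.89 is not delivered by the named test with the documents' own control figures. With 12 cases, 25 controls at 76% and alpha 0.05, power is 0.57 two-sided (0.62 one-sided) for a halving, which is 32 (27) points short. For a 50-point drop it is 0.82 (0.85), which is 7 (4) points short.

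The result under halving does not depend on the number of controls: at 1000 it is still no more than about 0.81. It does depend on the 76%, since a control prevalence near 95% would give about 0.90. Under the 50-point reading the shortfall with 25 controls disappears at about 40 to 50 controls. At the 10 or 9 children planned for Study 2, even that reading with 50 controls gives only 0.82 or 0.78 two-sided.

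**What to change.** In the SAP (Experiment 2) and protocol section 1.5:

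1. State the assumed control prevalence, the number of controls and their sources, the sidedness of the test, and whether 50% is relative or in percentage points (written as, for example, 76% to 38% or 76% to 26%).
2. Replace 0.89 with the Fisher power that follows. For 12 against 25, two-sided, that is about 0.57 for a halving or 0.82 for a 50-point drop.
3. Compute it at the Study 2 size actually planned, and reconcile the 12 in the power sentence with the 10 and 9 in protocol section 4.3. With 25 controls, two-sided, that gives about 0.47 under halving and 0.71 to 0.72 under a 50-point drop.
4. Report the per-case odds ratio with an exact confidence interval beside the Fisher p-value, so that a non-significant result shows how much benefit remains compatible with the data.

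The cost is a few sentences and a less favourable stated power. No extra participants or sessions are needed.
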